4.2. Secondary study parameter(s)

1. Values of biomarkers in the upper and lower airways of children with RSV infection and comparison with the values of these biomarkers in blood.

Values of biomarkers for (severe) RSV infection will be compared between upper and lower airways (in ventilated infants) and blood (all infants). Results will be compared within individual children and between children of different symptom severity categories (hospitalized non-ventilated, hospitalized ventilated and non-hospitalized infants with RSV infection).

2. Performance of currently used case definitions and severity measures for RSV infection in infants.

Clinical data about symptom severity of the participating infants will be compared with existing case definitions and severity measures. The performance of these case definitions and severity measures will be described as percentage agreement and percentage missed or incorrect diagnosis. In addition a new, simplified severity score (which will be developed within PROMISE and will be based on an extensive literature review and data obtained from the RESCEU infant studies) will be validated in this study.

3. Risk factors for severe RSV disease

Risk factors for severe RSV disease will be determined using demographic parameters, clinical parameters and outcome and laboratory test results of participating infants. Results will be displayed as categorical data with percentages or continuous variables with mean (+/-SD) and/or median (interquartile range). Comparisons between groups of different severity (hospitalized non-ventilated, hospitalized ventilated and non-hospitalized infants with RSV) and healthy controls will be performed using chi-square for categorical variables, Student-t-test for normally distributed continuous variables or Mann-Whitney U test for not normally distributed continuous variables. Multivariate regression analysis will be performed to analyse multiple risk factors for severe RSV disease.

4. Long-term sequelae of RSV infection in the first year of life

Long-term sequelae (amongst others recurrent wheeze) will be determined using the yearly questionnaires. Results will be displayed as categorical data with percentages or continuous variables with mean (+/-SD) and/or median (interquartile range). Comparisons between groups of different severity (hospitalized non-ventilated, hospitalized ventilated and non-hospitalized infants with RSV) will be performed using chi-square for categorical variables, Student-t-test for normally distributed continuous variables or Mann-Whitney U test for not normally distributed continuous variables.

5. Ethical considerations

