1.2. Objectives

Primary Objective:

- To validate biomarkers that are associated with severe RSV infection and respiratory sequelae.

Secondary Objective(s):

- To analyze dynamics of biomarkers in the upper and lower airways of children with RSV infection and compare these with blood
- To validate currently used case definitions and severity measures for RSV infection in infants

- To determine risk factors for severe RSV disease
- To determine long term sequelae of RSV infection in the first year of life

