4.1. Primary study parameter(s)

The primary endpoint is disease severity of RSV infection in the first year of life. The use of biomarkers that are associated with severe RSV infection and respiratory sequelae will be validated. RSV disease severity will be categorized in the following categories: hospitalized non-ventilated, hospitalized ventilated (PICU admitted) and non-hospitalized infants with RSV. If an infant was first recruited in the non-hospitalized group and is admitted during the course of RSV disease, the infant will be changed to the hospitalized non-ventilated or ventilated (PICU admission) group. In addition a control group of healthy controls will be used.

Large data sets are necessary for integrative computational analyses in order to identify profiles associated with disease severity. These data will come in a wide variety of formats depending on the sample being tested and the test being undertaken. In some cases analyses will be undertaken using standard techniques while others may require novel techniques. We will work closely together with other partners in the consortium.

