ANNEX I. ReSViNET score

Item	0 points	1 points	2 points	3 points
1 Feeding intolerance	No	Mild Decreased appetite and/or isolated vomits with cough.	Partial Frequent vomits with cough, rejected feed but able to tolerate fluids sufficiently to ensure hydration.	Total Oral intolerance or absolute rejection of oral feed, not able to guarantee adequate hydration orally. Required nasogastric and/or intravenous fluids
2 Medical intervention	No	Basic Nasal secretions aspiration, physical examination, trial of nebulized bronchodilators, antipyretics.	Intermediate Oxygen therapy required. Complementary exams were needed (chest X-rays, blood gases, hematimetry...). Maintained nebulized therapy with bronchodilators.	High Required respiratory support with positive pressure (either non-invasive in CPAP, BiPAP or high-flow O ₂ ; or invasive through endotracheal tube).
3 Respiratory difficulty	No	Mild Not in basal situation but does not appear severe. Wheezing only audible with stethoscope, good air entrance. If modified Wood Downes, Wang score or any other respiratory distress score is applied, it indicates mild severity.	Moderate Makes some extra respiratory effort (intercostal and/or tracheosternal retraction). Presented expiratory wheezing audible even without stethoscope, and air entrance may be decreased in localized areas. If modified Wood Downes, Wang score or any other respiratory distress score is applied, it indicates moderate severity.	Severe Respiratory effort is obvious. Inspiratory and expiratory wheezing and/or clearly decreased air entry. If modified Wood Downes, Wang score or any other respiratory distress score is applied, it indicates high severity.
4 Respiratory frequency	Normal < 2 m: 40–50 bpm 2–6 m: 35–45 bpm 6–12m: 30–40 bpm 12–24m: 25–35 bpm 24–36m: 20–30 bpm	Mild or occasional tachypnea Presented episodes of tachypnea, well tolerated, limited in time by self-resolution or response to secretion aspiration or nebulization.	Prolonged or recurrent tachypnea Tachypnea persisted or recurred despite secretion aspiration and/or nebulization with bronchodilators.	Severe alteration Severe and sustained tachypnea. Very superficial and quick breath rate. Normal/low breath rate with obvious increased respiratory effort and/or mental status affected. Orientative rates of severe tachypnea: < 2 m: > 70 bpm 2–6 m: > 60 bpm 6–12m: >55 bpm 12–24m: >50 bpm 24–36m: >40 bpm

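### Section 4.2 item 2 names no reference for validating severity measures; if level of care is the reference, ReSViNET item 2 shares content with it and agreement is likely to be overstated

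*Protocol*

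**What the plan says.** Protocol section 1.2 lists as a secondary objective "To validate currently used case definitions and severity measures for RSV infection in infants". Section 4.2 item 2 gives the analysis: "Clinical data about symptom severity of the participating infants will be compared with existing case definitions and severity measures". Performance "will be described as percentage agreement and percentage missed or incorrect diagnosis". The same item adds that a new simplified severity score will be validated in this study. It does not say which classification counts as correct.

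Section 4.1 defines severity by the care received: "RSV disease severity will be categorized in the following categories: hospitalized non-ventilated, hospitalized ventilated (PICU admitted) and non-hospitalized infants with RSV". Section 4.2 item 1 uses the same groups when it plans comparisons "between children of different symptom severity categories (hospitalized non-ventilated, hospitalized ventilated and non-hospitalized infants with RSV infection".

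The baseline visit text in section 2.2.1 has ReSViNET calculated at enrolment. In Annex I, item 2 of that score (medical intervention) gives 2 points for oxygen. It gives 3 points for this: "Required respiratory support with positive pressure (either non-invasive in CPAP, BiPAP or high-flow" oxygen, or an endotracheal tube. The top level of item 1 (feeding intolerance) describes oral intolerance and ends with a clause on care: "Required nasogastric and/or intravenous fluids".

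**The concern.** Percentage agreement and percentage missed can be computed only against a reference. The protocol defines one severity classification, level of care, and the item just before this one calls those groups symptom severity categories. Level of care is therefore the natural candidate. The one existing score the protocol names partly records level of care. An infant who is ventilated when scored receives the full 3 points on item 2 because of the ventilation, whatever the clinical signs show. This is incorporation bias: part of the index measure is also part of the standard it is judged against, which tends to push apparent performance up.

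At stake is how the secondary objective can be read. A favourable agreement figure could reflect how well the clinical signs grade severity, or it could reflect that treated infants get points for treatment. The protocol plans nothing that separates the two. The simplified score is exposed in the same way if it contains a treatment item; its content is not given.

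**Working it through.** The protocol states no performance figure for this objective, so there is no plan figure to reproduce. Two checks can be made.

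**1. Shared points (Annex I).** Six items carry up to 3 points and fever carries up to 2, so the maximum is 6 × 3 + 2 = 20. Item 2 is scored from care given: 3/20 = 15% of the maximum. Item 1 adds another 3 points at most, but its 0 to 2 point levels are symptoms and only one clause of its top level concerns care. The directly care-scored share is therefore 3 points, not 6.

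**2. Illustration of the effect of item 2 alone.** All distributions here are assumptions; none is in the protocol.
- Item 2, ventilated: always 3 (mean 3, variance 0).
- Item 2, hospitalised non-ventilated: 1, 2 or 3 with probability 0.2, 0.5, 0.3 (mean 2.1, variance 0.49).
- Item 2, non-hospitalised: 0, 1 or 2 with probability 0.2, 0.7, 0.1 (mean 0.9, variance 0.29).
- Sum of all other items: normal with the same mean in every group and SD 2, 3 or 4, so that it carries no information. Without item 2 the AUC is then 0.50.

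Formula (normal approximation): AUC = Φ(gap / √(v + 2·SD²)), where gap is the difference in item 2 means and v is the sum of the two item 2 variances.

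| Contrast | gap | v | SD 2 | SD 3 | SD 4 |
|---|---|---|---|---|---|
| Ventilated v non-hospitalised | 2.1 | 0.29 | 0.77 | 0.69 | 0.64 |
| Ventilated v hospitalised non-ventilated | 0.9 | 0.49 | 0.62 | 0.58 | 0.56 |
| Hospitalised non-ventilated v non-hospitalised | 1.2 | 0.78 | 0.66 | 0.61 | 0.58 |

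Example, first row, SD 2: Φ(2.1 / √(0.29 + 8)) = Φ(2.1 / 2.88) = Φ(0.73) = 0.77.

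**Check on one assumption.** Annex I gives 1 point for a physical examination, and the non-hospitalised group is medically attended, so a score of 0 there is doubtful. Moving that 0.2 to a score of 1 gives probabilities 0.9 and 0.1 for scores 1 and 2 (mean 1.1, variance 0.09).
- Ventilated v non-hospitalised: gap 1.9, v 0.09; Φ(1.9 / √8.09) = 0.75 at SD 2 and Φ(1.9 / √32.09) = 0.63 at SD 4.
- Hospitalised non-ventilated v non-hospitalised: gap 1.0, v 0.58; Φ(1.0 / √8.58) = 0.63 at SD 2 and Φ(1.0 / √32.58) = 0.57 at SD 4.

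The values fall slightly and the direction is unchanged.

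**The case against.** The strongest reply is that neither half of the comparison is fixed in the text. Item 2 of section 4.2 speaks of clinical data, and it is the only item in that section that does not list the care groups. ReSViNET is not named as a measure to be validated; it could itself be part of the clinical data. A reader might infer that the protocol has chosen level of care as the reference and that the validation will therefore be inflated. The document does not support that. It supports only a conditional statement, although the wording of section 4.1 and of section 4.2 item 1 makes the condition plausible.

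A reader might also infer that 6 of 20 points are an artefact of care, or that agreement would be high even if the clinical signs were useless. Neither follows. Item 1 is mainly clinical, so treating all of it as bias counts real feeding difficulty as error. For adjacent groups, the illustration gives an AUC of only 0.56 to 0.66 from item 2.

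The overlap is also incomplete. An infant on high-flow or CPAP without ventilation scores 3 on item 2 as well, hospital admission is not itself an item, and under section 4.1 an infant admitted later changes group while the score stays as calculated at enrolment. The planned metric is percentage agreement, for which no effect has been calculated.

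Finally, the choice of reference for a descriptive secondary objective could be made in a statistical analysis plan that is not shown. That is fair as to the choice itself. The shared content, however, lies within the protocol, between section 4.1 and Annex I, and remains whenever those two are compared.

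**Conclusion.** The point holds in conditional form. If level of care is the reference, ReSViNET and the reference share item 2 directly and one clause of item 1, and agreement is likely to be overstated. The size cannot be derived from the document. The AUCs under the working show a plausible order of magnitude only. They rest on the assumed item 2 distributions, on other items that carry no information, and on an AUC in place of the planned agreement percentages. The matter concerns a secondary objective and does not touch the primary biomarker comparison. It is worth correcting because the change is small and the likely error runs in the favourable direction.

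**What to change.** In section 4.2 item 2:
- Name the reference classification for each case definition and severity measure.
- Wherever a severity measure is compared with the level-of-care groups, report its performance for the full score and again without the item or items that record care given. For ReSViNET this is item 2. As a further sensitivity analysis, also leave out the whole of item 1, because a recorded 3 on that item does not show whether the tube or intravenous clause or the oral intolerance produced it.
- Base any claim that clinical signs discriminate severity on the version without item 2. The full score stays in the report, since the objective concerns measures as currently used.
- Apply the same rule to the new simplified score if it contains a treatment item.

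The cost is a few sentences of text, slightly more analysis and a less favourable reported performance. No new data are needed, provided the ReSViNET items are kept individually and not only as a total.

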1.3. Study design

This will be a monocenter, prospective, observational case-control study conducted across 2 consecutive years in the Wilhelmina Children's hospital and surrounding general practitioner (GP) offices and general hospitals. This case-control study will validate discovered biomarkers related to RSV infection susceptibility and disease severity in the RESCEU case-control study and birth cohort study. In addition, dynamics of the same biomarkers will be analysed in the upper and lower airways to better understand the sources of these biomarker signals. For this a validation cohort of previously healthy infants with different severities of RSV infection will be used and compared to healthy infants.

The following subgroups will be studied:

- Ventilated infants (n=40)
- Hospitalized, non-ventilated infants (n=40)
- Medically attended non-hospitalized infants (n=40)
- Healthy infants (n=40)

Children will be recruited during two RSV seasons. If RSV is suspected but not tested as part of routine care a point of care test for RSV will be done. Samples will be collected within 96 hours after hospitalization or start of symptoms in infants who are not admitted and repeated after 6-8 weeks (convalescence). Healthy infants will be recruited year round. Collection of samples of healthy controls will be done once. There will be annual follow up by questionnaire for up to 3 years.

Blood, stool, buccal, urine and nasopharyngeal samples will be obtained from all RSV positive infants at moment of infection and in convalescence 6-8 weeks later. In ventilated RSV positive infants, bronchoalveolar lavage (BAL) and/or tracheal aspirate samples will be obtained in combination with routine clinical care. Healthy infants will have blood, stool, buccal, urine and nasopharyngeal samples only at enrolment (i.e. there will be no follow up sampling).

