1.4.2. Inclusion criteria

In order to be eligible to participate in this study, a subject must meet all of the following criteria:

- Parents/legal guardians of infant are willing and able to give informed consent for participation in the study.
- Less than 12 months of age at enrolment.
- Hospitalized with (suspected) RSV infection for <96 hours at enrolment or within 96hrs of onset of illness (for those not admitted).*

* Not applicable for healthy control infants

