participants are informed about the study by member of the clinical team. If parents are interested in participating in the study, a member of the study team will provide verbal and written information about the study. Medical records will be screened to confirm eligibility for inclusion, either after full consent has been received or with verbal permission from the parent/guardian/legally authorised representative.

RSV point-of-care test

A molecular point-of-care test will be used for the quick identification of RSV in respiratory samples for eligibility to the study, when routine RSV diagnostics have not been performed.

Baseline visit

If RSV infection is confirmed, information will be collected on participant's medical history, any clinical examination performed and any laboratory and radiological investigations that are undertaken as part of routine medical care, and recorded on a case report form (CRF). A standardised respiratory clinical severity score (ReSViNET scale, appendix A (13)) grading the severity of the RSV disease will be calculated at enrolment. Clinical and health economic and quality of life data will be collected. An ARTI diary will be completed for 2 weeks from enrolment (RSV positive infants only).

At enrolment sampling will be done as follows (see also Table 2).

- Respiratory viral flocculated nasopharyngeal swab
- Synthetic absorption matrix [SAM] 2 nasal strips
- Nasopharyngeal bacterial swab
- Venous or capillary blood sample (maximum of ~0.8ml/kg)
- Urine sample (clean catch or from gauze in a nappy)
- Stool sample (from a "dirty" nappy)
- Buccal swab
- If the child is intubated and ventilated: BAL/tracheal aspirate

Subsequent Visits

One week after enrolment (healthy infants only):

One week after enrolment parents of participants will be contacted to assess if their infant developed any illness since enrolment.

Six to eight weeks (convalescent time point) (RSV positive infants only):

At 7 weeks (+/- 1 week) after discharge from hospital/emergency department, or 7 weeks post onset of symptoms for participants not attending hospital, participants will have one follow up visit. This will be a home visit by the study staff. If the child has an ARTI at that moment the follow-up visit will be postponed until the ARTI symptoms have disappeared.

At this time the recent respiratory health will be assessed and the following samples will be taken (see also Table 1):

- Respiratory viral flocculated nasopharyngeal swab

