- Synthetic absorption matrix [SAM] 2 nasal strips
- Nasopharyngeal bacterial swab

- Venous or capillary blood sample (maximum of ~0.8ml/kg)
- Urine sample (clean catch or from gauze in a nappy)
- Stool sample (from a “dirty” nappy)
- Buccal swab

Questionnaires

Baseline

- At inclusion a questionnaire about pregnancy, perinatal course and potential risk factors for RSV-hospitalization and sequelae will be filled in

One year of age

- Assessment of respiratory symptoms by parental questionnaire at age 1 year through telephone contact/email/online
- Cost, resource use and Health-Related Quality of Life (HRQoL) data will be collected using questionnaires for caregivers

Two years of age

- Assessment of respiratory symptoms by parental questionnaire at age 2 years through telephone contact/email/online
- Cost, resource use and HRQoL data will be collected using questionnaires for caregivers

Three years of age

- Assessment of respiratory symptoms by parental questionnaire at age 3 years through telephone contact/email/online
- Cost, resource use and HRQoL data will be collected using questionnaires for caregivers

Handling and storage of samples

See table 1 for volume and frequency of sampling. Samples will be stored at the biobank of the UMCU. During the study, samples will be shipped to other laboratories for analysis. Some samples will be sent to laboratories in countries within the European Union (EU) and some samples may be sent to laboratories in countries outside the EU for analysis.

- Sample handling and processing
- Serum: Blood will be drawn into serum collection tubes containing a clot activator and refrigerated between 2°C - 8°C for a maximum of 24 hours. Tubes will be centrifuged at 3000 rpm, 4°C for 10 minutes, serum extracted and stored at -80°C for later analysis.
- Whole blood: Whole blood will be collected in Natrium Heparin tubes and have appropriate buffers added and then be spun down and stored at -80C for later analysis.
- Functional Genomics: Whole blood will be added to Paxgene tubes containing a RNA stabilization reagent and stored at -80°C. Subsequently, RNA will be extracted and gene transcription determined using next generation sequencing approaches.

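### Section 4.2 item 3 does not limit candidate risk factors to variables that precede the illness, so consequences of severe RSV disease can be reported as its risk factors

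*Protocol*

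**What the plan says.** Protocol 1.2 makes risk factors for severe RSV disease a secondary objective. The analysis is in 4.2, item 3: "Risk factors for severe RSV disease will be determined using demographic parameters, clinical parameters and outcome and laboratory test results of participating infants". Item 3 compares the severity groups and the healthy controls with two-group tests, then adds: "Multivariate regression analysis will be performed to analyse multiple risk factors for severe RSV disease". It sets no rule on when a candidate variable must have been fixed.

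The outcome is defined in 4.1: "RSV disease severity will be categorized in the following categories: hospitalized non-ventilated, hospitalized ventilated (PICU admitted) and non-hospitalized infants with RSV".

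The timing comes from 1.4.2, "Hospitalized with (suspected) RSV infection for <96 hours at enrolment or within 96hrs of onset of illness (for those not admitted", and from 1.3, "Samples will be collected within 96 hours after hospitalization".

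Two streams of data bear on item 3 (Protocol 2.2.1):
- **Baseline visit.** Medical history, clinical examination, the ReSViNET score at enrolment, and "any laboratory and radiological investigations that are undertaken as part of routine medical care".
- **Questionnaire.** "At inclusion a questionnaire about pregnancy, perinatal course and potential risk factors for RSV-hospitalization and sequelae will be filled in".

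Separately, 1.3 and Table 1 plan research samples for every RSV-positive infant and, once, for every healthy control.

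**The concern.** A risk factor has to be in place before the severe disease that it is said to predict. Item 3 sets illness-time material beside demographics as the basis for finding risk factors. If severity itself moves a variable, a difference between severity groups in that variable shows what severe disease looks like. It does not show who was at risk.

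Two errors can follow. First, features of severe disease can be published as risk factors for it. Second, in the joint regression those features can take over part of the association that belongs to real pre-illness factors such as age or perinatal course. Item 3 also compares its variables with healthy controls, who have no RSV illness for such measurements to describe.

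This goes beyond a covariate list that a SAP could supply, because the protocol sentence itself names the classes of variables. A SAP that followed it faithfully would carry the problem.

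**Working it through.** The protocol gives no figure for this objective, so there is none to reproduce. The check is mainly one of timing.

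**Step 1. Timing of each class, for infants enrolled as inpatients**

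| Class of variable | Source in Protocol | Fixed before the illness? |
|---|---|---|
| Demographics, pregnancy, perinatal and potential risk-factor items | 2.2.1, Questionnaires | Yes |
| Medical history | 2.2.1, Baseline visit | Yes, for the part before the illness |
| Genotype from buccal swab | Table 1 | Yes |
| Clinical examination | 2.2.1, Baseline visit | No; recorded after admission |
| ReSViNET score | 2.2.1 and Annex I | No; calculated at enrolment, after admission |
| Routine laboratory and radiology results | 2.2.1, Baseline visit | No; also present only if care produced them |
| Illness-responsive research assays | 1.3 and Table 1 | No; sampled up to 96 hours after admission |

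Item 3 does not separate the first three rows from the rest.

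**Step 2. Overlap with the outcome.** Annex I gives 3 points on the medical-intervention item for positive-pressure support, including through an endotracheal tube. On the same item, the 2-point level includes "Complementary exams were needed (chest X-rays, blood gases, hematimetry" among its criteria. As a candidate risk factor, the score would partly restate the level of care that it is meant to explain.

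**Step 3. Different time origins.** The 96 hours run from admission for inpatients and from onset of illness for the others. Illness-time values can therefore differ between groups through stage of illness alone.

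**Step 4. How easily a consequence is declared a risk factor (illustration).** Input from the protocol: 40 infants per group. Assumed: two-sided alpha 0.05, SD 1, and a shift of d SD caused only by severity. Probability of p<0.05 ≈ Φ(d·√(40/2) − 1.960), with √20 = 4.472:
- d = 0.3: Φ(1.342 − 1.960) = Φ(−0.618) = 0.27
- d = 0.5: Φ(2.236 − 1.960) = Φ(0.276) = 0.61
- d = 0.8: Φ(3.578 − 1.960) = Φ(1.618) = 0.95
- d = 1.0: Φ(4.472 − 1.960) = Φ(2.512) = 0.99

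**Step 5. Attenuation of a genuine factor (simulation, all inputs assumed).** A binary pre-illness factor with 40% prevalence shifts latent severity by 0.5 SD. The most severe and the mildest infants are compared by logistic regression, 20,000 per group, without and with an illness-time marker whose correlation with severity is 0.5 to 0.85. The loss is 1 − (adjusted log odds ratio ÷ unadjusted log odds ratio).

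| Severe v mild | Odds ratio without marker | Loss of log odds ratio |
|---|---|---|
| Top 2% v bottom 50% | 5.1 | 6–19% |
| Top 5% v bottom 80% | 3.4 | 10–37% |
| Top 10% v bottom 60% | 3.4 | 9–30% |

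In a repeat run the ends of these ranges moved by up to 8 percentage points. The direction was the same throughout.

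**Step 6. Selective availability of routine laboratory results (simulation, all inputs assumed).** A marker has no true group difference but correlates 0.5 with illness intensity within groups. All 40 infants in the severe group have a value. If only the sickest 50% of the mild group are tested (20 of 40), a difference is declared in about 31% of studies; if only the sickest 25% (10 of 40), in about 41%. The nominal rate is 5%.

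**The case against.** The best defence is that item 3 is one loosely worded sentence in a secondary objective, that covariate rules usually belong to a SAP, and that the regression sentence does not say which variables enter. That is fair as far as it goes: the document does not establish that illness-time variables will enter the model, only that nothing keeps them out of a list that names their classes.

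Several stronger readings are tempting, and the protocol does not support them:
- **That laboratory values exist only where care required them.** This is true of routine results. Research samples are planned for all RSV-positive infants and for healthy controls, although limited blood volume may force some blood tests to be prioritised. A reader might infer that up to 80 of 160 infants (40 non-hospitalised and 40 controls) have no laboratory values. That could apply to routine results only.
- **That all item 3 data postdate the severity level.** Demographic, perinatal and genetic variables precede illness. Under 4.1, infants recruited as non-hospitalised and later admitted are regrouped, so their baseline data precede the final category.
- **That outcome is being offered as a predictor.** The word may simply mean the severity outcome being modelled. The phrase is ambiguous, and clinical parameters and laboratory results remain on the list either way.
- **That genuine factors would be dismissed.** In the Step 5 table the loss is partial, and its size depends on the assumed cut-offs and correlation.

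**Conclusion.** The point holds as a defect in what item 3 admits, not as a prediction of what will be reported. For infants enrolled as inpatients, illness-time clinical findings, the ReSViNET score and illness-responsive laboratory values are recorded once at least the hospitalised level has been reached. Item 3 accepts them as a basis for naming risk factors.

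The conclusion on timing needs no assumption beyond the protocol's own definitions of severity and enrolment. The size does. Moderate shifts of 0.5 to 0.8 SD caused purely by severity would be declared significant with probability 0.61 to 0.95 at 40 per group. A genuine factor might lose roughly 6% to 37% of its log odds ratio. Neither range is a document figure, and both would change with other assumptions. The selective-testing problem is confined to routine-care results. The primary biomarker objective is not affected, since it asks for association with severity and does not require variables that precede it.

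**What to change.** Amend Protocol 4.2, item 3 as follows:
1. Restrict candidate risk factors and the multivariate model to variables fixed before the illness: demographics, age, medical history before the illness, the pregnancy, perinatal and potential risk-factor items of the baseline questionnaire, and genotype if used.
2. State that *outcome* means the severity category being modelled.
3. Report illness-time clinical parameters, severity scores, and illness-responsive or routine laboratory results in a separate table by severity group. Label them as characteristics of severe disease and keep them outside the risk-factor model.
4. For item 3, compare healthy controls on pre-illness variables only. State that biomarker comparisons under the primary objective are unchanged.

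The cost is a few sentences. The questionnaire in 2.2.1 already collects the pregnancy, perinatal and potential risk-factor data, and no sample, visit or infant is added. The one thing given up is a combined prognostic model under item 3 that uses illness-time variables. If that is wanted, it should be a separate analysis, named as prognostic.
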